Single Pulse Recruitment Curves: Single-pulse recruitment curves will be used to assess motor cortical excitability. 70 monophasic TMS stimuli in posterior-anterior current direction ranging in intensity from 60% to 150% (15% increments) of resting motor threshold will be used to generate recruitment curves. Order of stimulation intensity will be randomized. Trials with pre-stimulus electromyography activity (100-ms prior to TMS) in excess of 15 μ V will be discarded and repeated at the end of the 70 trials.

Short Afferent Inhibition: Short-latency afferent inhibition will be used to index sensory projections to motor cortex. Short-latency afferent inhibition has been used to investigate the contributions of different intracortical M1 networks to motor learning. Pilot data from our group shows that directing attention to a high visual attention load task selectively alters short-latency afferent inhibition in the

Study Title: Modulating interaction of motor learning networks in rehabilitation of stroke

motor network recruited by monophasic anterior-posterior current. This oligosynaptic motor network is the same network that has been linked to cerebellar mediated procedural learning and may be a prime substrate of declarative influence over procedural learning post-stroke.

Short-latency afferent inhibition within the ipsilesional motor cortex will be assessed using both anterior-posterior and posterior-anterior monophasic test stimuli over the extensor hotspot. 20 trials for each current direction will be preceded by median nerve stimulation (20ms interval, 3x sensory threshold) . Test stimulus intensity will be set to the intensity that elicits a motor evoked potential in the extensor carpi radialis of ~1mV for that current direction. An additional 20 trials for each current direction will be conducted in the absence of median nerve stimulation to serve as the unconditioned baseline. The same procedure will be repeated for contralateral motor cortex. In the event that sensory threshold cannot be established for the paretic limb median nerve stimulation intensity will be set to that of the non-paretic limb. In the event that a motor evoked potential of ~1mV cannot be evoked in the targeted limb stimulator output will be set to the minimal stimulator output at which extensor carpi radialis motor evoked potential amplitude stabilizes.

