The statistical approach and power analyses were developed in consultation with the Center for Statistical Consulting and Research at the University of Michigan. For Specific Aim 1 (**Determine whether cTBS over contralesional dorsolateral prefrontal cortex prior to motor practice enhances motor learning post-stroke**) the primary outcome metric will be response time during random reaches. The extent of sensorimotor procedural knowledge will be assessed using an Arm (active-cTBS, sham-cTBS) x Session (Session 2, Session 6) repeated measures ANOVA. The extent of procedural knowledge relating to the larger movement sequence will be assessed using a Arm (active-cTBS, sham-cTBS) x Sequence (Random, Repeated) x Session (Session 2, Session 6) repeated measures ANOVA. As a secondary assessment, the rate of procedural learning will be assessed for each measure by including Sessions 3, 4 and 5 as levels of the factor Session. An Arm (active-cTBS, sham-cTBS) x Session (Session 1, Session 6) repeated measures ANOVA will be used to assess time to complete the Jebsen-Hand Function Test

For Specific Aim 2 (**Determine the effects of cTBS over dorsolateral prefrontal cortex upon motor networks**) two separate sets of analyses will be performed. First, separate Arm (active-cTBS, sham-cTBS) x Hemisphere x Time (Session 1, Session 6) repeated measures ANOVA will be performed to assess change in intracortical motor networks (recruitment curves, short-latency afferent inhibition) across study arm. Motor evoked potential amplitude will be the dependent variable. Arm x Hemisphere x Time interactions will be decomposed using separate Arm x Time repeated measures ANOVAs for each Hemisphere.

Second, to assess changes in intercortical neural networks group level maps for each identified component in the independent component analysis will be assessed using separate Arm x Sequence random-effects analysis for Session 1 and Session 6. Statistical threshold will be set to $p < 0.05$ and corrected for multiple comparisons using the false discovery rate.

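### The Aim 2 test of short-latency afferent inhibition is run on evoked-potential amplitude, with no conditioned-to-unconditioned contrast, so as written it does not measure inhibition

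*Combined protocol and SAP*

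**What the plan says.** The analysis is in Statistical Analyses and Power, under Specific Aim 2. It reads: "First, separate Arm (active-cTBS, sham-cTBS) x Hemisphere x Time (Session 1, Session 6) repeated measures ANOVA will be performed". Its purpose is to "assess change in intracortical motor networks (recruitment curves, short-latency afferent inhibition) across study arm". The outcome is then fixed in one sentence: "Motor evoked potential amplitude will be the dependent variable". The follow-up keeps the same terms: "Arm x Hemisphere x Time interactions will be decomposed using separate Arm x Time repeated measures ANOVAs for each Hemisphere".

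The data are described under TMS Assessments, Short Afferent Inhibition. Two current directions are used, anterior-posterior and posterior-anterior. For the conditioned trials, "20 trials for each current direction will be preceded by median nerve stimulation". For the comparison trials, "An additional 20 trials for each current direction will be conducted in the absence of median nerve stimulation to serve as the unconditioned baseline". The test pulse is set to give a response of about 1 mV for each direction. Where that cannot be reached, "stimulator output will be set to the minimal stimulator output at which extensor carpi radialis motor evoked potential amplitude stabilizes". The procedure is repeated on the other hemisphere.

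No section defines a ratio, a difference or a conditioning factor. The Aim 3 paragraph lists ipsilesional afferent inhibition as a predictor, again without a definition.

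**The concern.** Afferent inhibition is a relative quantity: how far median nerve stimulation reduces the response below its size without that stimulation. The design collects both halves of the comparison, but the stated model uses neither a contrast nor a ratio. Amplitude alone is the product of test-response size and the degree of inhibition, and the model cannot separate them.

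At stake is what an Arm x Time result would mean. If the unconditioned response grows after active stimulation and inhibition stays the same, amplitude changes and could be reported as altered inhibition. If inhibition weakens while the test response shrinks, the two can cancel and a real effect is missed. Leaving the index open also permits a choice between ratio, difference and current direction after the data from 16 people have been seen. The Aim 3 predictor inherits the same gap.

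**Working it through.** **The plan's own figure.** The only sample-size figure covering Aim 2 is 5 to 12 participants (power 0.80, alpha 0.05, correlation 0.7), raised to 16. With f² = η²/(1 − η²), λ = f²·N·m/(1 − 0.7), and m = 6 measurements in one group (the plan does not state m, so this is an assumption):
- η² = 0.06: f² = 0.0638; N = 12 gives λ = 0.0638 × 12 × 6 / 0.3 = 15.3 and power 0.83.
- η² = 0.16: f² = 0.1905; N = 5 gives λ = 0.1905 × 5 × 6 / 0.3 = 19.0 and power 0.85.

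So 5 to 12 is reproduced and is not in dispute here. The effect sizes behind it concern response time and motor or sensory improvement. No stated power covers afferent inhibition.

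**Cells collected against cells modelled.** Per participant: 2 conditioning x 2 current directions x 2 hemispheres x 2 sessions x 2 arms = 32. The stated model has 2 x 2 x 2 = 8. Conditioning and current direction are the factors left out.

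**Arithmetic of the mixing.** Let T be the unconditioned amplitude and r the conditioned-to-unconditioned ratio. Amplitude averaged over both trial types is T(1 + r)/2; conditioned amplitude alone is T·r. Assume T = 1 mV and r = 0.5, so the average is 0.75 mV.
- Inhibition changes, r = 0.7: the ratio moves 40%, but the average moves to 0.85 mV, or 13.3%.
- Only the test response changes, T = 1.2 mV: the average moves to 0.90 mV, or 20%, with no change in inhibition.
- Both change, r = 0.7 and T = 0.882 mV: the average is 0.882 × 1.7 / 2 = 0.75 mV. An 11.8% fall in T hides the whole effect.

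**Rejection rates.** The contrast is Arm x Time within one hemisphere, n = 16, two-sided 0.05, with independent errors and the change placed in Session 6 of the active arm. The documents give no SDs. The range assumed is 0.1 to 0.4 mV for T and 0.10 to 0.20 for r, with 20,000 simulated trials per setting.

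| Outcome analysed | Only T rises 20%, inhibition unchanged | r moves from 0.5 to 0.7 |
|---|---|---|
| Amplitude, both trial types averaged | 13% to 84% | 9% to 53% |
| Amplitude, conditioned trials only | 9% to 36% | 23% to 90% |
| Conditioned minus unconditioned amplitude | 9% to 35% | 27% to 92% |
| Ratio | about 5% | 46% to 96% |

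**Hand check at the middle setting** (SD of T 0.2, SD of r 0.15), averaged amplitude, T rising 20%:
- Cell variance = (1.5² × 0.04 + 0.0225 + 0.04 × 0.0225)/4 = 0.02835.
- The raised cell has 1.44 times that, 0.0408.
- Contrast SD = √(3 × 0.02835 + 0.0408) = 0.355.
- Standardised effect = 0.15/0.355 = 0.42, which at n = 16 gives 35%, matching the simulation.

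For the ratio moving by 0.2, the contrast SD is 2 × 0.15 = 0.30, the effect is 0.67 and power is 70%, again matching.

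The third row shows that adding a conditioning factor to raw amplitude is only a partial remedy: a difference in millivolts still scales with T.

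**The case against.** **The ratio was probably intended.** Calling the unconditioned trials a baseline points that way, and Aim 3 treats inhibition as a single score. That is fair as to intent, but the outcome sentence names amplitude. Elsewhere the plan writes such steps out: Jebsen scores are normalised to the other limb, and Sequence is a factor in Aim 1.

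**The 1 mV target controls test-response size.** It limits the problem. It does not remove it: the target is approximate, there is a fallback when it cannot be met, and the plan does not say whether intensity is reset at each session.

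**The loss from using amplitude depends on undocumented values.** This stands. On the log scale, take a ratio SD of 0.25 and a ratio test with 80% power (standardised effect 0.75). Conditioned amplitude then has 74%, 59% and 44% power at test-response log-SD 0.1, 0.2 and 0.3. If 0.10 of that ratio SD is sampling error in the denominator, the amplitude SD at log-SD 0.1 is √(0.25² − 0.10² + 0.1²) = 0.25. Power is then 80%, with no loss, and 64% and 46% at the two larger values.

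**Stronger readings a reader might infer, which the documents do not support:**
- *That recruitment curves have the same fault.* Their stated purpose is motor cortical excitability; slope and gain are not mentioned. Mean amplitude over seven equally spaced intensities is close to an area under the curve and serves that purpose.
- *That a smaller ipsilesional test response reverses the result.* A stable difference in size between hemispheres is not itself an Arm x Time effect, which is what the follow-up tests.
- *That the two current directions are pooled.* Separate ANOVAs could mean one per direction; the text does not say. Only if they are pooled, and the posterior-anterior effect is null, does 80% power fall to 51%, 41% or 35% at between-direction correlations of 0, 0.3 and 0.6 (assumed). Separate runs would still lack a conditioning contrast.
- *That the plan expects an effect confined to the anterior-posterior network.* The pilot finding that attention "selectively alters short-latency afferent inhibition in the" network recruited by that current comes from a visual-attention task. The protocol says only that this network may be a substrate.

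**Conclusion.** The concern holds for short-latency afferent inhibition, and the stated outcome is wrong as written rather than merely short on detail. An Arm x Time effect on amplitude cannot be attributed to inhibition. It can appear when inhibition is unchanged and can be absent when inhibition has changed.

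The direction of the problem follows from the definition of inhibition and needs no assumption. Its size does: the rejection rates above rest on T = 1 mV, a ratio of 0.5, independent errors and the stated SD ranges, and they treat the ratio as observed with its own SD. A false signal in the averaged-amplitude analysis would be a real change in amplitude carrying the wrong label.

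This should be fixed, but it is confined to the mechanistic aim and one Aim 3 predictor. The Aim 1 response-time outcome, the sample size and the data collection do not depend on it.

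**What to change.** In Statistical Analyses and Power, Specific Aim 2, replace the dependent variable for afferent inhibition with the log of the ratio of mean conditioned to mean unconditioned amplitude, computed per participant, hemisphere, session, arm and current direction. Run the Arm x Hemisphere x Time ANOVA, with its Arm x Time follow-up, separately for anterior-posterior and posterior-anterior current. Amplitude can remain the outcome for recruitment curves.

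In the Aim 3 paragraph, define ipsilesional afferent inhibition as the same ratio at Session 1, and say which current direction supplies it or that both are reported. Whether one direction is named as principal is the investigators' choice.

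The cost is analysis wording and one additional ANOVA. Every trial needed is already in the protocol.

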Resting State Functional Magnetic Resonance Imaging: T2*-weighted blood-oxygen level dependent scans (single-shot EPI, TR=2000ms, TE=30ms, flip angle $\theta = 90^\circ$, FOV=220x220mm, voxel dimension=3.4x3.4x3.2mm, 40 slices, 10 min/scan) will be acquired during Session 1 and Session 6 of each study arm. During these scans patients will lay supine with their eyes fixed on a white cross presented upon a black background. Temporal correlations in spontaneous metabolic demand between neuroanatomical regions in the resting state infer task-related functional connectivity in healthy individuals and those post-stroke . Reductions in resting state functional connectivity have been demonstrated in motor networks within and across hemisphere post-stroke (for a review see) and are predictive of rehabilitation outcomes . Therefore, we will use resting state functional connectivity to quantify changes neuronal networks underlying procedural learning (Aim 2) and whether pre-intervention resting state functional connectivity within the motor network may predict intervention outcomes (Aim 3).

Study Title: Modulating interaction of motor learning networks in rehabilitation of stroke

Resting state data will be preprocessed as part of the standard processing stream at the University of Michigan that includes: removal of k-space outliers, field map corrections for inhomogeneity, removal of cardiac and respiratory rhythm, low pass filtering of data, slice time correction and motion correction (MCLIFRT, fMRIB software library) . Following pre-processing, the ARtifact detection tools (ART) toolbox will be used to identify global mean intensity outliers. An independent components analysis (Melodic, FSL) will be used to identify spatially distinct resting state networks including the motor, dorsal attention and default mode networks as well as any other networks that may be present.

Statistical Analyses and Power

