Targeted enrollment for Aim 1 (Behavior) and Aim 2 (Motor networks) is 16 participants. This number was derived using effect sizes from our previous work. We observed effect sizes (partial η^2) for two-way repeated measures Stimulation Site x Session interactions of 0.135 (M1-cTBS vs. Control) and 0.107 (S1-cTBS vs. Control) when comparing response time from early practice to a delayed retention test. Brodie et al. observed effect sizes for motor and sensory improvements pre- to post an S1-5Hz repetitive TMS intervention that ranged between medium (partial $\eta^2 = 0.06$) to large (partial $\eta^2 > 0.16$). Based upon these effect sizes, the targeted enrollment that provides a power of 0.80 at an alpha level of 0.05 with a correlation of 0.7 among the repeated measures is between 5 and 12 participants (G*Power). These numbers are consistent with previously published work using similar cross-over designs to investigate the efficacy of M1 non-invasive brain stimulation interventions upon both behavior and M1 physiology post-stroke (i.e. recruitment curves and short-latency- afferent inhibition). In these studies sample sizes range from 6-16 stroke patients. To

Study Title: Modulating interaction of motor learning networks in rehabilitation of stroke

account for effect sizes within the lower range of our estimates, overestimates of the correlations between the different levels in our repeated measures design as well as experimental mortality (see **Potential Problems and Alternative Strategies**), we will target 16 individuals.

With respect to the measures of resting state functional connectivity (Aim 2), the majority of work post-stroke has been aimed at determining differences in network functional connectivity compared to non-stroke control individuals. To our knowledge, no studies have assessed changes in resting state connectivity across an intervention similar to that proposed here. The closest approximation is a longitudinal study looking at functional connectivity between ipsilesional and contralesional M1 post-stroke. This study (n=12 patients) demonstrated significant differences between 1, 3 and 6 months post-stroke. Therefore, 16 individuals should be sufficient to detect any changes in functional connectivity associated with our intervention.

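### The resting-state connectivity analysis for Aim 2 names a factor that fixation scans do not have and contains no Arm x Session term, so the test of change is not specified

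*Combined protocol and SAP*

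**What the plan says.** All references are to the combined protocol and SAP.

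- **Statistical Analyses and Power, Specific Aim 2.** With the stated purpose of assessing change in networks between cortical regions, the group maps for each independent component "will be assessed using separate Arm x Sequence random-effects analysis for Session 1 and Session 6". The threshold is p < 0.05 with false discovery rate (FDR) correction.
- **Same section, Specific Aim 1.** Sequence appears as a defined factor only here, in an "Arm (active-cTBS, sham-cTBS) x Sequence (Random, Repeated) x Session (Session 2, Session 6) repeated measures ANOVA" of response time.
- **Same section, TMS part of Aim 2.** The recruitment-curve and afferent-inhibition measures get an Arm "x Hemisphere x Time (Session 1, Session 6) repeated measures ANOVA will be performed to assess change in intracortical motor networks".
- **Resting State Functional Magnetic Resonance Imaging.** Scans are taken at Session 1 and Session 6 of each arm, to quantify change in the networks behind procedural learning. "During these scans patients will lay supine with their eyes fixed on a white cross presented upon a black background".
- **Sample-size text for resting state.** The plan says that "no studies have assessed changes in resting state connectivity across an intervention similar to that proposed here". It then reasons from a 12-patient longitudinal study: "Therefore, 16 individuals should be sufficient to detect any changes in functional connectivity associated with our intervention".

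**The concern.** Two things do not fit. First, random and repeated reaches are conditions of the touch-screen task. Nobody reaches in the scanner, so a resting scan cannot be assigned to either level. Second, a model fitted separately at Session 1 and at Session 6 compares the arms within each session but does not compare the sessions. It therefore cannot test whether connectivity changed more under active than under sham stimulation. That is the goal given in the imaging section, in the analysis sentence itself and in the sample-size text.

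At stake is which test will carry the connectivity conclusion. If this is settled only after the maps have been seen, the analyst can choose between tests that often disagree.

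**Working it through.** **1. No figure to reproduce.** The plan gives no effect size, SD or power for connectivity. The check is a reading of the text, followed by an illustration on stated assumptions.

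**2. What the data allow.** Each participant has four scans: two arms by two sessions. Let D1 and D6 be the within-person active-minus-sham differences at Session 1 and Session 6. Analyses run separately by session test the mean of D1 and the mean of D6. Change by arm is D6 − D1, which neither analysis estimates. The univariate mixed model under Potential Problems and Alternative Strategies does not supply it, because it is only an option if participants are lost between arms.

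**3. The possible readings.**

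- *Literal:* Sequence is random versus repeated. The model cannot be fitted.
- *Slip for Session*, with separate meaning one model per component: an Arm x Session model, tested on D6 − D1.
- *Cross-over order*, one model per session: a coherent arm contrast at Session 6 (D6), but no test of change. The Design section calls this concept order, not sequence.

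**4. How far the two workable tests differ.** Inputs from the plan: n = 16, and a correlation of 0.7 ("with a correlation of 0.7 among the repeated measures", a general input, not a connectivity figure). Assumed: effect 0.5 SD, 8 participants per order, order fitted (14 df), one uncorrected value, two-sided 5%, no carry-over, and r = correlation of D1 with D6. A common correlation of 0.7 among all four scans implies r = 0.

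- SD of D1 or D6 = √(2 × (1 − 0.7)) = 0.775.
- SD of D6 − D1 = 0.775 × √(2(1 − r)) = 1.095, 0.775, 0.600 at r = 0, 0.5, 0.7.
- Noncentrality = 0.5 × √16 / SD = 2.58 for D6, and 1.83, 2.58, 3.33 for D6 − D1.

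| Test | r = 0 | r = 0.5 | r = 0.7 |
|---|---|---|---|
| Session 6 contrast, unadjusted | 67% | 67% | 67% |
| Arm x Session interaction | 40% | 67% | 87% |
| Session 6 adjusted for Session 1 (simulated, 13 df) | 64% | 76% | 89% |

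At r = 0, Session 6 versus interaction is 30% versus 18% for an effect of 0.3 SD, and 97% versus 78% for 0.8 SD. With 12 completers and 0.5 SD, noncentrality is 2.24 and 1.58 on 10 df, giving 52% versus 30%. At n = 16, leaving order out (15 df) moves the 67% and the interaction figures by less than half a percentage point.

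In simulation, the unadjusted Session 6 test and the interaction reach different verdicts on the same data in 31% to 35% of trials with the 0.5 SD effect. With no effect they disagree in 7% to 9%, and each rejects in about 5%.

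**5. Carry-over.** Suppose a fraction c of the effect from an active first arm is present at Session 1 of the second arm, and a fraction k of that remains at its Session 6. Averaging over the two orders, with a true effect of 0.50:

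- mean D1 = −0.5c/2
- mean D6 = 0.5(1 − kc/2)
- interaction = 0.5(1 + c(1 − k)/2)

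| Full carry-over (c = 1) | Session 6 | Interaction |
|---|---|---|
| persists (k = 1) | 0.25 | 0.50 |
| halves (k = 0.5) | 0.375 | 0.625 |
| gone by Session 6 (k = 0) | 0.50 | 0.75 |

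The adjusted contrast is mean D6 − r × mean D1. At c = 1, k = 1 it equals 0.25 + 0.25r: 0.375 at r = 0.5 and 0.425 at r = 0.7. It is biased toward zero at every r below 1.

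**The case against.** The strongest reply is that this is a one-word drafting error. The response-time, Jebsen and TMS models in the same section all cross Arm with Session or Time, so an Arm x Session intent can be inferred. Alternatively, sequence is a usual cross-over word for order. Arm by order at each session is then a sensible model: Session 6 gives the post-intervention contrast, Session 1 checks baseline or carry-over, and Aim 2 speaks of effects. The plan also does not name the decisive term for its other ANOVAs, so that omission is general style.

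Much of this stands. The point is about wording, and it would be too strong to say that no reading works: the order reading yields a coherent contrast. But the reply offers two different repairs, the documents do not choose between them, and the order reading still leaves change untested.

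A reader might also infer that separate session tests would produce false positives from a standing gap between arms. The documents do not support that. Participants are their own controls in counterbalanced order, so without carry-over no gap is expected at Session 1, and each test holds about 5% when there is no effect. Nor is the interaction always the better test, as the power table shows.

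Finally, the power figures are not evidence from this trial. The effect, r and the carry-over fractions are assumed, FDR-corrected maps would have lower power, and 16 completers is optimistic because the target of 16 already allows for dropout.

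**Conclusion.** The point holds as a specification defect. The sentence cannot be executed with Sequence as the plan defines it. Read literally, it contains no test of the change in connectivity that the plan sets out to measure, and no other section repairs it. The two plausible intentions are different tests, whose ranking by power reverses at r = 0.5 under the assumptions above and which respond differently to carry-over. Those figures show only that the choice matters; they do not predict this trial's power.

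The scope is the connectivity half of Aim 2. A reader might take the defect to weaken the trial's main result. It does not: the Aim 1 primary outcome, response time during random reaches, and the TMS ANOVAs have their own stated models. It should be fixed before the maps are analysed.

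**What to change.** Replace the sentence with: *one Arm (active-cTBS, sham-cTBS) x Session (Session 1, Session 6) random-effects analysis per component; the Arm x Session interaction is the FDR-corrected test of change.* This has the same Arm x Session form as the random-reach response-time and Jebsen models.

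An acceptable alternative is to pre-specify the Session 6 arm contrast adjusted for Session 1. Name one of the two in advance and state the carry-over assumption behind it. A term for arm order or period is a separate, optional addition; no other model in the section has one.

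The cost is wording only, since all scans are already planned. Each option has a downside. With weakly correlated arm differences and no carry-over, the interaction loses power against the unadjusted Session 6 contrast (illustratively 40% versus 67%, or 30% versus 52% with 12 completers). If carry-over fades during the second arm, the interaction is biased upward. If carry-over persists unchanged, the interaction is unbiased but the adjusted Session 6 contrast is biased toward zero.

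### The 5-to-12-participant power basis applies a correlation of 0.7 on top of partial eta-squared values that appear to contain it already, so it does not support the planned Arm x Session test as written

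*Combined protocol and SAP*

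**What the plan says.** All of this is in the combined protocol and SAP, under Statistical Analyses and Power.

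- Primary test for Aim 1: "The extent of sensorimotor procedural knowledge will be assessed using an Arm (active-cTBS, sham-cTBS) x Session (Session 2, Session 6) repeated measures ANOVA". Learning rate, a secondary question, is addressed "by including Sessions 3, 4 and 5 as levels of the factor Session".
- Effect sizes from the team's previous work: partial eta-squared values from "two-way repeated measures Stimulation Site x Session interactions of 0.135 (M1-cTBS vs. Control) and 0.107 (S1-cTBS vs. Control", comparing early practice with delayed retention.
- Effect sizes from a cited study: "effect sizes for motor and sensory improvements pre- to post an S1-5Hz repetitive TMS intervention", running from 0.06 to above 0.16.
- Result: at alpha 0.05, the number for 80% power "with a correlation of 0.7 among the repeated measures is between 5 and 12 participants (G*Power".
- Target: 16. The stated reason is that this number should "account for effect sizes within the lower range of our estimates, overestimates of the correlations between the different levels in our repeated measures design", with experimental mortality named too. No dropout rate and no power figure accompany this.
- Connectivity: the support is a single longitudinal study. "This study (n=12 patients) demonstrated significant differences between 1, 3 and 6 months post-stroke", from which the plan concludes that "16 individuals should be sufficient to detect any changes in functional connectivity associated with our intervention".

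**The concern.** The power statement gives no number of measurements, degrees of freedom, effect-size option or source for the 0.7. That matters because partial eta-squared can enter a repeated-measures power calculation on different scales. On one scale the effect is expressed against the raw SD of each measurement, and the correlation is then used to shrink the error. On another, the value comes from the within-subject error term of a fitted ANOVA, and the correlation is already in it. Using a value of the second kind as if it were of the first makes the trial look much better powered than it is.

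The team's own two values are described as observed results of repeated-measures interactions, which points to the second kind. This is the only power basis given for the primary test, and the claim that 16 leaves a margin for smaller effects, a lower correlation and dropout builds on it.

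**Working it through.** **Inputs.** Alpha 0.05, power 0.80, r = 0.7, partial eta-squared (η²) 0.06, 0.107, 0.135 and 0.16, target 16: all from the sample-size paragraph. The planned test is a 2 x 2 fully within-person interaction, so it has 1 and n − 1 df. Effect: f² = η²/(1 − η²) = 0.0638, 0.1198, 0.1561, 0.1905. Power is from the noncentral F distribution with noncentrality λ.

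**1. Reproducing 5 to 12.** For an omnibus within-person factor with m measurements, λ = f²·n·m/(1 − r), with df m − 1 and (n − 1)(m − 1).

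- m = 6 (5 df): n = 12 / 7 / 6 / 5. This matches exactly, but it is not the planned test: the planned Session factor for response time has two levels, or five with Sessions 3 to 5 added.
- m = 2: n = 21 / 12 / 10 / 9. This gives 12 at 0.107, and 5 only from about 0.30, which an open-ended upper value above 0.16 does not rule out.
- Four cells, 1-df contrast, effect on the raw cell-SD scale: λ = 4·n·f²/(1 − r). At 0.06 and n = 12, λ = 4 × 12 × 0.0638/0.3 = 10.2 and power is 83%. Required n = 12 / 8 / 6 / 6, reaching 5 from about 0.18.

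Each of these applies r = 0.7 to the quoted values. Without r, even a 3-df omnibus test over four measurements needs 59 at 0.06.

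**2. What the four-cell setting implies.** The partial eta-squared it assumes for the tested contrast is g/(1 + g), with g = 4f²/0.3. For 0.06 / 0.107 / 0.135 / 0.16 this is 0.46 / 0.62 / 0.68 / 0.72. The plan describes no such conversion.

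**3. The planned 1-df test under each reading.**

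- *Direct*: the value is already the partial eta-squared of the within-person contrast, so λ = n·f².
- *Between-group*: the value compares change between separate groups. For a paired test, λ = 2·n·f²/(1 − ρ), where ρ is the correlation between the two arms' change scores. If all four response times correlate equally at 0.7, the covariance of the two change scores is proportional to 0.7 − 0.7 − 0.7 + 0.7 = 0, so ρ = 0.

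| Reading | n for 80% at 0.06 / 0.107 / 0.135 / 0.16 | Power at n = 16 |
|---|---|---|
| Four-cell, r = 0.7 | 12 / 8 / 6 / 6 | 93%, then over 99% |
| Between-group, ρ = 0.7 | 21 / 12 / 10 / 9 | 68 / 92 / 97 / 99% |
| Between-group, ρ = 0.5 | 33 / 19 / 15 / 13 | 47 / 74 / 84 / 90% |
| Between-group, ρ = 0 | 64 / 35 / 28 / 23 | 27 / 45 / 55 / 64% |
| Direct | 125 / 68 / 53 / 44 | 16 / 25 / 32 / 37% |

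Example for 0.107 at n = 16: direct, λ = 16 × 0.1198 = 1.92; between-group with ρ = 0, λ = 2 × 16 × 0.1198 = 3.83. Against the critical F(1, 15) = 4.543, these give 25% and 45%.

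**4. The margin in 16, on the most favourable (four-cell) reading at 0.06.** Completer counts below 16 are assumed dropout.

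- r = 0.65 with 14 completers: 84%
- r = 0.6 with 15: 82%
- r = 0.6 with 14: 79%
- r = 0.6 with 12: 71%

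**5. What 16 can detect, without any disputed input.** For a paired contrast with standardised difference d, λ = n·d². Power reaches 80% at d = 0.75 for n = 16, which is partial eta-squared 0.75²/(1 + 0.75²) = 0.36, and at d = 0.89 for n = 12.

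**6. Connectivity.** No calculation is given. The cited n = 12 study followed connectivity between the two primary motor cortices over months after stroke, without this intervention. The plan here is group maps for every identified component, with false discovery rate correction. A significant result in the former does not establish power for the latter.

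**The case against.** The strongest reply is that 5 to 12 is a legitimate software result. It reproduces exactly with six measurements and almost exactly for the planned contrast with four cells, and enrolment was then set above the range. That stands: a reader might infer an arithmetic error, and there is none.

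It is also fair that the prior error term is not described. A comparison of a stimulation site with control, crossed with session, could come from separate groups. On that reading power at 16 for the team's own effects runs from 45% and 55% up to 92% and 97%, depending on a change-score correlation that the plan does not give. A reader might therefore take 25% and 32% as the trial's actual power. The documents do not establish that; it is one reading among several.

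A reader might also infer that 16 leaves no room for a lower correlation and dropout together. On the four-cell reading that is not so: modest joint shortfalls keep 80%, and only larger ones fail.

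Finally, the plan openly says that no comparable connectivity study exists and calls its source an approximation. The fault there is confined to the concluding sentence. Nothing in the documents says that a null result would be read as adequately powered.

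**Conclusion.** Wrong as written: the power basis is unsupported because of an apparent effect-size-scale mismatch, not an arithmetic slip. No route to 5 to 12 was found that does not apply r = 0.7 to values which, as described, would normally already reflect it. The double counting remains an inference until the saved software settings are seen, and it would fall away if the values had been converted to the raw-SD scale beforehand.

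On the two natural readings of the team's own effects (direct, or between-group with the equal 0.7 correlation that the plan assumes), the 1-df test needs 28 to 68 participants rather than 5 to 12, and 16 gives 25% to 55% power. Higher power requires either the raw-SD scale or a positive change-score correlation, and the plan states neither. This does not show that 16 is the wrong number to enrol; it shows that the stated justification does not carry it. The connectivity sentence is a separate and smaller overstatement.

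**What to change.** Keep n = 16. Replace the 5-to-12 statement with:

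> n=16 completers gives 80% power (two-sided 0.05) to detect an Arm x Session difference of 0.75 SD of the within-person difference in change (partial eta-squared 0.36 for that contrast); with, for example, 12 completers, 0.89 SD.

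If the prior effect sizes are kept, state the number of measurements, the df, the effect-size option and the source of 0.7. Also give power at n = 16 for change-score correlations of 0, 0.5 and 0.7. Limit the sentence on low effects, correlations and mortality to what those figures support.

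Replace the concluding connectivity sentence with:

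> The connectivity analyses are not formally powered.

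The 0.75 SD figure should not be carried over to the connectivity maps, which are analysed as Arm x Sequence separately by session.

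The cost is rewording and one check of the saved power settings, with no added participants. The downside is that the stated power becomes less favourable.
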